# 7.8 EFFICACY ANALYSIS

The primary and secondary endpoints will be derived from the daily diary data entered by patients.

Two-sided tests at a significance level of  $\alpha$ =5% will be used throughout unless otherwise stated. The null hypothesis is that lubiprostone is equal to placebo against the alternative that lubiprostone is different to placebo. All analyses will be performed using the FAS. Analyses specified for the PP are to be regarded as supportive evidence. There will be no adjustment for multiplicity.

All efficacy endpoints will be summarized by treatment and visit. If baseline measures are also defined and collected for an efficacy endpoint then change from Baseline at each visit will also be presented by summary statistics by treatment and visit. Change from baseline will be calculated as (post-baseline value) – (baseline value). Baseline is defined as the last recorded measurement prior to treatment.

For diary data, baseline values will be the average of all diary data from the screening period (Days -14 through -1, inclusive, relative to day of first dose). If more than 14 days of diary data are collected during the screening period only the data from Day -14 onwards will be used. If fewer than 8 days are available then the baseline value will be set to missing.

Centers may be pooled geographically if necessary for analysis purposes. This will be determined before database lock.

CROSS-REGIONAL TEMPLATE				
Template Number:	C-TMPL-DO-801	Page:	20 of 31	
Version Number:	1.2	Effective Date:	14 Sep 2015	
This version replaces:	1.1			
Parent Document:	C-SOP-DO-800			
Template Title: S	statistical Analysis Plan (Legacy Takeda)			

For weekly SBM frequency, at least 4 days of diary data are required to compute a weekly estimate, if there are less than 4 days recorded in a week then the SBM frequency for that week will be set to missing.

As the primary endpoint is within the first week of study treatment and only 4 days of diary collection are required it is not anticipated that missing values should be a cause of concern therefore the LOCF technique will be used to impute missing values for efficacy analysis purposes only. For a given subject, the most recent nonmissing data point will be carried forward to the subsequent week where data are missing. Details for each efficacy parameter are given below. It is expected, based on previous studies, that the number of subjects with in-sufficient post baseline data for the primary endpoint will be small therefore a simple approach to handling missing data will be used. Where there is no post baseline efficacy data then the baseline value will be used, it is expected that the number of SBMs should increase for those on treatment, therefore using a baseline value for missing post baseline data assumes no treatment effect, this approach can be considered conservative,. To examine the effect of the requirement to have at least a minimum of 4 days post baseline efficacy data for the primary endpoint, using the stratified van Elteren test [2], will be conducted using all valid SBM data post baseline even when less than 4 days data is present, only where there is no post baseline data will baseline be used in this analysis.

An SBM is defined as any BM that does not occur within 24 hours after rescue medication use. Certain periods after taking rescue medication will be defined as "blackout periods" during which BMs are considered as non-spontaneous. Blackout periods, including those with missing or partial times for rescue medication use in the diary, will be handled as follows:

0-24 hours post rescue medication intake if the time is fully specified.

0-24 hours post rescue medication intake if the hour is present, but the minute is missing. The blackout time will commence from the imputed time. If the minutes are incomplete or missing from either the rescue medication or bowel movement entry then it is assumed that the missing values are zero and an imputed time will be calculated. e.g.

1	5	_	_	=	1	5	0	0
2	1	5		=	2	1	5	0

0-48 hours, beginning from midnight on the day the rescue medication intake is recorded for, if the hour is missing from the time entry for the rescue medication.

Box plots will be produced for each weekly measure (SBM frequency, mean degree of straining, mean degree of stool consistency and weekly abdominal symptoms scores) by treatment over time from baseline to Week 4. Additionally graphs presenting histograms of SBM frequency will also be produced by treatment for each week.

CROSS-REGIONAL TEMPLATE				
Template Number:	C-TMPL-DO-801	Page:	21 of 31	
Version Number:	1.2	Effective Date:	14 Sep 2015	
This version replaces	: 1.1			
Parent Document:	C-SOP-DO-800			
Template Title:	Statistical Analysis Plan (Legacy Takeda)			

7.8.1 Primary Efficacy Endpoint(s)

The primary efficacy endpoint is SBM frequency at Week 1; an SBM is defined as any BM that does not occur within 24 hours after rescue medication use. Since rescue medication use will be disallowed during Week 1, the SBM frequency should equal the BM frequency. In the case of protocol violators, the analysis will be based on SBMs.

In order to adjust for early withdrawals or those with less than 7 days diary data, weekly SBM frequency will be calculated as follows:

7 x (Number of SBMs / Number of days)

Where the number of days is the number of days during the week that the subject was in the study. Weeks will be calculated as 168-hour intervals starting from the day after randomization (Day1), if there is no time recorded for the morning dose on Day1 then the time of the first recorded morning dose will be used. The number of days will generally be 7 unless a subject drops out during a treatment week. If the number of days is less than 4, then the data will be considered insufficient and the frequency will be missing.

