# 4.1.4 Summary of Clinical Data

Lubiprostone has been approved for use in patients with chronic idiopathic constipation since January 2006 and been marketed in the United States (US) under the trade name Amitiza since April 2006 for CIC, irritable bowel syndrome (IBS) with constipation and for opioid-induced constipation. Other approvals include: Japan, Switzerland, the United Kingdom, Ireland, Belgium, Luxembourg and the Netherlands.

Lubiprostone has been administered to humans in at least 30 clinical studies.

The pivotal phase 3 studies included 2 multicenter, double-blind, randomized, placebo-controlled, efficacy and safety studies (SC0131 and SC0232) for the treatment of

occasional constipation conducted in the US, and 1 placebo-controlled study (SC0831) in subjects with CIC conducted in Japan.

In SC0131 and SC0232, the efficacy and safety of a 24  $\mu$ g twice daily (BID) dose of lubiprostone was compared with placebo. In both studies, following a 2-week Baseline/Washout Period, subjects received 4 weeks of double-blind medication. No dose escalation was permitted during either study. Each study was powered to detect a difference of 2 spontaneous bowel movements (SBMs) between the placebo and lubiprostone groups after 1 week of treatment. The primary and secondary efficacy endpoints were the same in both studies. The overall mean number of days on study drug was 27.1 days for SC0131 and 26.8 days for SC0232. The mean actual daily exposure was 1.9 capsules/day in both the placebo and lubiprostone groups in both studies. In terms of dose, the median actual daily exposure in the lubiprostone group was 46  $\mu$ g in both SC0131 and SC0232.

SC0131 evaluated 242 subjects, and SC0232 evaluated 237 subjects. In the primary efficacy analysis in each study, the mean SBM frequency during Week 1 was significantly higher (p<0.0001) in the lubiprostone group than in the placebo group.

The overall treatment effect across all weeks was also significant (p<0.0001) in both studies. In SC0131, the median number of SBMs at Week 1 was 3.0 in the placebo group and 5.0 in the lubiprostone group; in SC0232, the values were 3.5 and 5.0, respectively. In both studies, the baseline median number of SBMs in both treatment groups was 1.5.

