# CONFIDENTIAL

- 3. The subject is an immediate family member, study site employee, or is in a dependent relationship with a study site employee who is involved in conduct of this study (eg, spouse, parent, child, sibling) or may consent under duress.
- 4. The subject has, in the judgment of the investigator, clinically significant abnormal hematological parameters of hemoglobin, hematocrit, or erythrocytes at Screening.
- 5. The subject has a history or clinical manifestations of significant mechanical obstruction (intestinal obstruction due to tumor, hernia etc).
- 6. The subject has a history of hypersensitivity or allergies to lubiprostone or any of its excipients.
- 7. The subject has a history of drug abuse (defined as any illicit drug use) or a history of alcohol abuse within 1 year prior to the Screening Visit.
- 8. The subject is required to take excluded medications as listed in Section 7.3.1.
- 9. If female, the subject is pregnant or lactating or intending to become pregnant before, during, or within 1 month after participating in this study; or intending to donate ova during such time period.
- 10. Subject whose constipation is considered to be due to drugs or to whom a prohibited concomitant medication has been administered.
- 11. Subject having chronic constipation due to a secondary cause (medications, diabetes mellitus, hypothyroidism, depression, etc.)
- 12. Subject in whom there is sufficient criteria for irritable bowel syndrome (IBS) or functional defecation disorder.
- 13. Subject whose SBM frequency is 3 or more per week.
- 14. Subject whose SBM frequency has been less than 3 times per week for less than 6 months in duration or whose symptoms associated with SBM have been present for less than 6 months (hard feces, sensation of incomplete evacuation, or straining).
- 15. Subject who received treatment with a rescue medication within 24 hours prior to the first dose in the morning of Day 1: bisacodyl suppository, which is a standard laxative, glycerin enema, or any other rescue medication.
- 16. Subject who has megacolon/megarectum or has received a diagnosis of intestinal pseudo-obstruction.

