### CONFIDENTIAL

- Has chronic constipation due to a secondary cause (medications, diabetes mellitus, hypothyroidism, depression, etc).
- Has sufficient criteria for IBS or there is a functional defecation disorder.
- SBM frequency is 3 or more per week.
- SBM frequency has been less than 3 times per week for less than 6 months in duration or whose symptoms associated with SBM have been present for less than 6 months (hard feces, sensation of incomplete evacuation, or straining).
- Received treatment with a rescue medication within 24 hours prior to the first dose on the morning of Day 1.
- Has megacolon/megarectum or has received a diagnosis of intestinal pseudo-obstruction.
- Has confirmed or suspected organic disorders of the large intestine (obstruction, stenosis, carcinoma, or inflammatory bowel disease). Any subject in whom total colonoscopy has detected a polyp requiring treatment is excluded from this study.
- Has been hospitalized for gastrointestinal or abdominal surgery within 3 months before the start of this study.
- Use of any excluded medications, procedures or treatments prior to the assessment of the primary endpoint.

Any other significant event interfering with efficacy evaluation of primary endpoint, to be decided at the Targeted Data Review Meeting.

Subjects will be assigned to the treatment group dependent upon the actual treatment randomized and received.

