# 7.2 ANALYSIS SETS

Total Set: The total set consists of all subjects who signed the informed consent form, including subjects withdrawn prior to randomization.

Full Analysis Set (FAS): This will consist of all subjects randomized to receive study treatment whether or not they received treatment. Subjects will be reported according to their randomized treatment group regardless of treatment received.

Per-Protocol Analysis Set (PPS): The PPS will consist of subjects in the FAS with the additional following criteria for exclusion:

- Did not receive study treatment as per randomization schedule (including not receiving any randomized treatment)
- Dose of randomized treatment was adjusted.

CROSS-REGIONAL TEMPLATE				
Template Number:	C-TMPL-DO-801	Page:	14 of 31	
Version Number:	1.2	Effective Date:	14 Sep 2015	
This version replaces	s: 1.1			
Parent Document:	C-SOP-DO-800			
Template Title:	Statistical Analysis Plan (Legacy Takeda)			

- Violated inclusion criteria, such as:
  - Does not have a history of constipation defined as SBM frequency of less than 3 times per week on average for 6 months or longer (and observed during Screening Period).
  - Does not have SBMs with  $\geq 1$  of the following 3 symptoms for the last 6 months or longer, in at least 1 out of every 4 bowel movements: scybalum stool or hard feces, straining, or the sensation of incomplete evacuation.
  - The subject rarely has loose stools without the use of laxatives.
- Violated exclusion criteria, such as:
  - The subject has a history or clinical manifestations of significant mechanical obstruction (intestinal obstruction due to tumor, hernia etc).
  - Has chronic constipation due to a secondary cause (medications, diabetes mellitus, hypothyroidism, depression, etc).
  - Has sufficient criteria for IBS or there is a functional defecation disorder.
  - BM frequency is 3 or more per week.
  - SBM frequency has been less than 3 times per week for less than 6 months in duration or whose symptoms associated with SBM have been present for less than 6 months (hard feces, sensation of incomplete evacuation, or straining).
  - Received treatment with a rescue medication within 24 hours prior to the first dose on the morning of Day 1.
  - Has megacolon/megarectum or has received a diagnosis of intestinal pseudoobstruction.

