## 7.13 CHANGES IN THE STATISTICAL ANALYSIS PLAN

This SAP provides more details for the protocol specified analyses and includes additional analysis not presented in the protocol..

	CRUSS-REGIONAL TEMPI		
Template Number:	C-TMPL-DO-801	Page:	31 of 31
Version Number:	1.2	Effective Date:	14 Sep 2015
This version replaces	: 1.1		
Parent Document:	C-SOP-DO-800		
Template Title:	Statistical Analysis Plan (Legacy Takeda)		

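### Two SAP statements conflict with the protocol: a per-protocol exclusion that says BM where SBM is meant, and a primary-endpoint sentence that says rescue is barred throughout Week 1 (minor)

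*SAP*

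**What the plan says.** **Per-protocol set.** Under the heading "Violated exclusion criteria, such as", SAP 7.2 lists "BM frequency is 3 or more per week". Exclusion criterion 13 in Protocol 7.2 reads "Subject whose SBM frequency is 3 or more per week", and the per-protocol list in Protocol 13.1.1 reads "SBM frequency is 3 or more per week". SAP 7.13 declares no change of rule. It says only: "This SAP provides more details for the protocol specified analyses and includes additional analysis not presented in the protocol".

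**Rescue in Week 1.** SAP 7.8.1 states "Since rescue medication use will be disallowed during Week 1, the SBM frequency should equal the BM frequency" and continues "In the case of protocol violators, the analysis will be based on SBMs". SAP 4.2 and Protocol 2.0, 6.1, 7.3.2.1, 8.1.1.2 and 9.3.2 all set a shorter bar, from 24 hours before to 48 hours after the first dose. Protocol 9.3.2 lets a rescue prescription be given on Day -1, with the next visit 7 days after first dose. The responder definition in SAP 7.8.2 makes anyone who uses rescue in a given week, Week 1 included, a non-responder for that week.

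**The concern.** Total BMs and SBMs differ only through rescue, and rescue is permitted during Screening. A PPS rule stated in BMs is therefore stricter than the eligibility rule it is meant to mirror, and could remove a subject who met every entry criterion. The set concerned is the supportive one: SAP 7.2 uses the PPS only for the primary variable.

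The 7.8.1 sentence is a false premise in the section that governs the primary FAS analysis. It also bears on PPS membership. Laxatives are on the excluded list (Protocol 7.3.1), with rescue as the stated exception (7.3.2.1). SAP 7.2 excludes from the PPS anyone who used an excluded medication before the primary assessment, and leaves other events to a data review meeting. A meeting that has been told that Week 1 rescue was disallowed could treat compliant users as violators.

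**Working it through.** **1. The plan's own figure.** SAP 6.0 gives means of 4 and 5.9, SDs of 2.7 and 4, 90% power and two-sided alpha of 0.05.
- Pooled SD = √((2.7² + 4²)/2) = √11.645 = 3.41.
- The two-sample t-test for a difference of 1.9 needs 68.76 per arm. Dividing by the Wilcoxon efficiency 3/π gives 72.01, rounded up to 73 per arm, or **146** in total, as stated.
- 146/0.97 = 150.5, so 151 against the stated 150, a difference of one subject.

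Neither disputed wording enters this calculation, so correcting both leaves 146 and 150 as they are.

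**2. The BM bullet.** Screening lasts 14 days. Weekly rate = count ÷ 14 × 7.
- 5 SBMs: 5/14 × 7 = 2.5 per week, which is eligible.
- 5 SBMs + 1 rescue-induced BM = 6 BMs: 6/14 × 7 = 3.0 per week, which meets the bullet as written.
- For the two US phase 3 studies, Protocol 4.1.4 reports that "the baseline median number of SBMs in both treatment groups was 1.5". Taking this as a weekly figure (an assumption), such a subject has 3 SBMs in 14 days and would need 6 − 3 = 3 rescue-induced BMs to meet the bullet.

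As an illustration, assume Screening SBM frequency is normal with mean 1.5 and SD 0.8 (close to Protocol Table 4.a), truncated to between 0 and 3. The share of such eligible subjects reaching 3 BMs per week is then:

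| Rescue-induced BMs per week (assumed) | Share with BM ≥ 3 |
|---|---|
| 0.5 | 8% |
| 1 | 25% |
| 2 | 75% |

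These shares apply only to subjects who have that many rescue-induced BMs. If rescue users tend to be those with the fewest SBMs, the true shares are lower. No Screening rescue rate is given, so the shares cannot be turned into a number of subjects.

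**3. The Week 1 bar.** Week 1 is 168 hours from the first dose and the bar covers the first 48. (168 − 48)/168 = 120/168 = 71.4% of the week lies outside it. This counts hours, not subjects. Rescue also requires 3 consecutive days without an adequate BM, so 71% is an upper bound on the permitted time.

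**4. Does the 7.8.1 sentence change the count?** SAP 7.8.1 defines an SBM, and the weekly rate is 7 times the number of SBMs divided by days in study. SAP 7.8 sets blackout periods after rescue for every subject. None of these rules depends on whether a user is called a violator, so the FAS value is the same either way.

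**The case against.** The BM bullet is an example under a heading about violated exclusion criteria. No exclusion criterion uses total BM frequency, so a subject who meets only the BM wording has violated nothing. The neighbouring bullets say SBM, and Protocol 13.1.1 requires the analysis sets to be identified and exclusions documented before database lock. The list is loose elsewhere too: its loose-stools bullet restates an inclusion criterion as if it were a violation. All this stands, and it makes a wrong exclusion less likely. It does not make the bullet correct. A letter lost in converting the PDF cannot be ruled out, so the signed SAP should be checked first. If that reads SBM, this half of the point falls away.

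For 7.8.1, the sentence states an expectation and not a counting rule. That also stands. A reader might infer that BMs will be counted for compliant rescue users, because SBMs are named only for violators, and that primary power would fall. The documents do not support this. It would mean departing from the stated SBM formula and blackout rules, and any figure for the loss would need Week 1 rescue rates that the documents do not give.

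A reader might equally infer that both errors are confined to the per-protocol analysis. That is not right for 7.8.1, which sits in the primary FAS section, although its practical effect would be on PPS review.

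Finally, SAP 4.2 ties the three-day rescue rule to the Screening Period, which might look like a third SAP error and some support for 7.8.1. Protocol 6.1 carries the same wording and conflicts with Protocol 2.0, 7.3.2.1 and 8.1.1.2, so the SAP inherited it. The post-dose bar itself presupposes rescue during treatment, since a 48-hour limit would otherwise be pointless.

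**Conclusion.** Both conflicts are real and minor. The BM bullet is wrong as written and touches only the supportive PPS analysis of the primary endpoint. The 7.8.1 statement is wrong about the rescue rule. It leaves the FAS primary analysis intact provided the SBM formula and blackout rules are followed, but it could mislead the PPS review. In each case the number of subjects affected is unknown. The example of 5 SBMs plus 1 rescue-induced BM shows only that a wrong exclusion is possible. No stated figure changes.

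**What to change.** In the SAP 7.2 PPS list, restore SBM in place of BM. In SAP 7.8.1, replace the two sentences with wording such as:

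> Rescue is barred from 24 hours before to 48 hours after the first dose. The analysis uses SBMs for all subjects, and BMs in a blackout period do not count as SBMs. Later Week 1 use of standard rescue (bisacodyl suppository, glycerin enema or an equivalent) under the protocol's rule is not in itself a violation.

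The text refers to the blackout period and not to 24 hours, because SAP 7.8 extends it to 48 hours when the hour of rescue is missing. It names standard rescue only. Third-line rescue taken from the excluded list stays with the blinded data review.

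Do not edit SAP 4.2 alone. If the Screening Period wording is to be clarified, change it in Protocol 6.1 and SAP 4.2 together.

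The cost is wording edits in two SAP sections before unblinding. The two edits need no protocol amendment, new data or new analyses.

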## Primary Analysis

Since outliers are commonly observed in these data, parametric models may not be robust. The efficacy data will therefore be analyzed by a van Elteren test stratified by center. If necessary, small centers will be pooled as mentioned above. This procedure will test the null hypothesis of equal SBM rates between treatments at the end of Week 1 versus the alternative hypothesis of non-equality between the 2 groups; the test will be conducted at a 2-sided significance level of 0.05. A related 95% confidence interval and point estimate will be provided for the treatment difference; the confidence interval will be estimated by inverting the hypothesis test. This endpoint will be analyzed for the FAS.

# Sensitivity Analyses

The primary analysis as described above will be repeated using the PP rather than the FAS. An additional sensitivity analysis using the FAS assuming a 'worse-case' scenario approach will also be conducted, where missing values, including those with < 4 days diary data, are assigned the worst case values (the lowest SBM frequency for week 1) recorded in the study by any subject for that endpoint at that time.

Additionally the endpoint will be analyzed using robust analysis of variance (ANOVA) models (by M-estimation [3] using PROC ROBUSTREG in SAS) with center and treatment in the model as a sensitivity analysis using the FAS. The interaction between treatment and center will also be examined in a separate model, using robust ANOVA methods as previously described.

To examine the effects of any permanent dose reduction in response to an AE (as recorded on the eCRF) an additional sensitivity analysis will also be performed. This will be performed on the

CROSS-REGIONAL TEMPLATE			
Template Number:	C-TMPL-DO-801	Page:	22 of 31
Version Number:	1.2	Effective Date:	14 Sep 2015
This version replaces:	1.1		
Parent Document:	C-SOP-DO-800		
Template Title: St	tatistical Analysis Plan (Legacy Takeda)		

FAS where data from those subjects with a dose reduction will be excluded from the time of dose reduction (taken as date of last BID dose + 12 hours, e.g. if the evening dose is removed then the time will be from the morning dose + 12 hours, if the morning dose is removed then it will be from the previous day's evening dose + 12 hours) and subjects will be treated as a dropout from this time point onwards. This will be implemented using robust ANOVA. Additionally, another factor will be added to the robust ANOVA model to examine the effect of dose reduction (), this will be performed on the FAS. This analysis will not be carried out if the number of subjects with a dose reduction within the first week is less than 5%.

